To provide clinical access to ⁶⁸Ga-PSMA-11 PET at the University of Colorado. Patients will be monitored for safety.

Secondary Objective(s):

To compare the diagnostic impact of ⁶⁸Ga-PSMA-11 PET/CT imaging over current standard of care imaging modalities.

To compare the impact of ⁶⁸Ga-PSMA-11 PET/CT imaging over standard of care imaging on the therapeutic decision or change in management with regards to the number and/or lesion location and PSA levels.

Exploratory Objective(s):

Obtain preliminary data on accuracy of 68Ga-PSMA-11 PET/CT imaging PET / MRI in patients with intermediate and high-risk prostate cancer patients prior to prostatectomy.

METHODOLOGY	
Study Design	This is a prospective, Phase III, single-center, open-label to provide extended access in patients with biochemically recurrent prostate cancer. Eligible patients will undergo baseline assessments as per the Schedule of Study Activities in Appendix A. Approximately 100 patients are planned for enrollment in this study. Patients will receive a single dose of ⁶⁸ Ga-PSMA-11 and undergo a PET/CT or PET/MRI imaging study.
Intervention	The intervention is a PET scan with the radiolabelled PSMA ligand, ⁶⁸ Ga-PSMA-11. The PET may be combined with a CT scan as a PET/CT or an MRI scan as PET/MRI. ⁶⁸ Ga-PSMA-11 PET/CT will be acquired using a modern digital GE PET/CT scanner or a modern digital PET / MRI scanner.
Intervention Duration	AEs will be collected during injection and uptake phase (45-120 min posts infusion) of Ga-68 PSMA-11 PET/CT scan. All safety events will be recorded up to 120 min post injection.
Population	Men with pathologically proven prostate adenocarcinoma, high risk cancer at diagnosis, evidence of biochemical recurrence, or known metastatic disease planned to start and change systemic therapy regimen
Investigational Agent and Formulation	A description of the components of the PSMA-11 Sterile Cold Kit can be found in Section 5.1 of the protocol and in the initial IND submission.
Dose and Route of Administration	One intravenous catheter will be placed for radiopharmaceutical administration. Patients will be injected with 100 MBq (3mCi)-300 MBq(7mCi) of ⁶⁸ Ga-PSMA-11 via this catheter.

SUBJECT POPULATION	
Number of Patients Planned for Enrollment	Approximately 100 patients are planned for enrollment in this study.
Major Inclusion Criteria	
Patients must meet all inclusion criteria to be considered eligible for participation in the study.
 
• Histopathologically proven prostate adenocarcinoma.• Age \geq 18 years• 1) Patients with newly diagnosed with prostate cancer: Primary Staging: high / intermediate risk per NCCN guidelines or 2) Biochemical Recurrence: Rising PSA after definitive therapy with prostatectomy or radiation therapy (external beam or brachytherapy) or other local therapies:
• Post radical prostatectomy (RP) – AUA recommendation PSA greater than or equal to 0.2 ng/mL measured more than 6-13 weeks after RP and confirmed by a second determination of a PSA level of >0.2 ng/mL• Post-radiation therapy – ASTRO-Phoenix consensus definition Nadir + greater than or equal to 2 ng/mL rise in PSA• After Local Therapies Nadir + greater than or equal to 2 ng/mL rise in PSA or3) Metastatic prostate cancer, castrate naïve or castrate resistant:
• To confirm suspected metastatic disease in patients with recurrent prostate cancer• To assess treatment response of metastatic disease• Ability to understand a written informed consent document, and the willingness to sign it.

Name of Sponsor		[name]
Investigational Product		68 Ga-PSMA-11 prepared using a PSMA-11 Sterile Cold Kit
Major Exclusion Criteria	
• Unable to lie flat, still or tolerate a PET/CT scan, or any other condition that would preclude PET/CT imaging.• Patients with any medical condition or circumstance that the investigator believes may compromise the data collection or lead to a failure to fulfil the study requirements.• Patients with known hypersensitivity to the active substance or to any of the excipients of the investigational product.	
ASSESSMENTS		
Efficacy	Standard of care imaging, clinical assessment, PSA.	
Safety	Safety of the drug has been established (11). AEs will be collected during injection and uptake phase (45-120 min post infusion) of Ga-68 PSMA-11 PET/CT scan. All safety events will be recorded up to 120 min post injection.	

TABLE OF CONTENTS

SYNOPSIS.....	4
ABBREVIATIONS AND DEFINITIONS	10
1. BACKGROUND AND RATIONALE	11
1.1 Name and Description of Investigational Product.....	13
1.2 Results of Nonclinical Studies	13
1.3 Results of Clinical Studies	13
2. STUDY OBJECTIVES.....	13
2.1 Primary Objective	13
2.2 Secondary Objectives.....	13

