4. INVESTIGATIONAL PLAN

4.1 SUBJECT SELECTION

4.1.1 Eligibility Criteria

- Histopathologically proven prostate adenocarcinoma
- Age \geq 18 years
- Patients already diagnosed with prostate cancer: Primary Staging: intermediate and high-risk patients per NCCN guidelines
- Biochemical Recurrence: Rising PSA after definitive therapy with prostatectomy or radiation therapy (external beam or brachytherapy):
 - a. Post radical prostatectomy (RP) – AUA recommendation
 - i. PSA greater than or equal to 0.2 ng/mL measured more than 6-13 weeks after RP and confirmed by a second determination of a PSA level of >0.2 ng/mL
 - b. Post-radiation therapy – ASTRO-Phoenix consensus definition
 - i. Nadir + greater than or equal to 2 ng/mL rise in PSA
- Ability to understand a written informed consent document, and the willingness to sign it.

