4.2.3 Selection and Timing of Dose for Each Subject

No specific patient preparation is required before ⁶⁸Ga-PSMA-11 injection. The imaging agent (Ga-68 PSMA-11) will be administered on an outpatient basis. It will be administered a single time intravenously prior to the PET imaging. The injected dose will be 100 to 300 MBq (~3-7 mCi) of ⁶⁸Ga-PSMA-11.

Following a waiting period of 60 minutes post 68Ga-PSMA-11 administration, patients will be scanned from mid thighs to base of the skull. Images will be acquired with patients in a supine position with their arms raised above their head. If patients cannot raise their arms above the head, the arms will be comfortably positioned and secured by the side of the patient. The goal is to administer this amount of the imaging probe labeled with 2.5 MBq of ⁶⁸Ga per kg body weight with a minimum of 100 MBq (3mCi) and maximum of 300 MBq (7mCi) 68Ga per patient. The typical acquisition time per bed position will be 3 min and the typical number of bed positions is 4.

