4.4 IMAGE ANALYSIS AND INTERPRETATION

A board-certified nuclear medicine physician or nuclear radiologist on-site will interpret the images of the ⁶⁸Ga-PSMA-11 PET/CT scan. Images will be corrected for attenuation and scatter and adjusted for system sensitivity and will provide parametric images in terms of standardized uptake values (SUV) (= MBq found/gm tissue / MBq injected/gm body mass).

PET imaging can be combined with a low-dose CT for attenuation correction, a diagnostic CT (PET/CT), or MRI (PET/MR). Patients may undergo a diagnostic MRI of the prostate, other body parts or a whole-body MRI at the same imaging session as clinically indicated. Contrast material may be administered for the CT or MRI as clinically indicated.

Imaging will be initiated at approximately 60 minutes (45-120 minutes) following administration of the PSMA radiopharmaceutical. At the discretion of the investigator, an additional image of the pelvis may be obtained.

Patients will receive a single dose of ⁶⁸Ga-PSMA-11 and undergo a PET/CT or PET/MRI imaging study. At the time of interpretation of the ⁶⁸Ga-PSMA-11 PET study, the reviewing nuclear medicine physician and/or radiologist will compare the ⁶⁸Ga-PSMA-11 PET findings with the results from previously performed standard-of-care imaging for prostate cancer staging. The presence or absence of sites suspicious for recurrent prostate cancer will be documented. (e.g., prostate bed, lymph nodes, metastases to bone or other organs).

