4.5.2 Secondary Objective

Determine rate of overall changes in management by comparing planned management strategy using conventional imaging with executed management strategy incorporating information from ⁶⁸Ga-PSMA-11 PET/CT, regardless of treatment modality.

Analysis: The rate of change in management based on the incorporation of ⁶⁸Ga-PSMA-11 PET/CT results will be expressed as the percentage of total patients imaged in which change in management occurred, regardless of treatment modality. The rate of change in management will also be estimated within each group (initial staging, biochemical recurrence, and pre/post treatment). 95% confidence intervals (CIs) will be used to express precision of the estimates.

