4.5.3 Sample Size and Power Estimate

Since this protocol is for clinical access only, there is no need for sample size and power estimation calculations. It is anticipated that 100 patients will be imaged with primary diagnosis of prostate cancer or biochemically recurrent prostate cancer. There will likely be a ramp up period in the number of patients who will be scanned.

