6.2.11 EXTENT OF EXPOSURE

A total of 100 patients are planned for exposure to a single dose of ⁶⁸Ga-PSMA-11 at 100MBq (3mCi)-300 MBq (7mCi).

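### Section 3.1.2 pools men scanned for treatment response into PSMA positivity by PSA and against earlier conventional imaging, mixing the change of modality with change over the interval

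*Combined protocol and SAP*

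**What the plan says.** **Entry.** The Synopsis (Major Inclusion Criteria, third route, metastatic disease) lists "To assess treatment response of metastatic disease" among the reasons for a scan. Its Population row describes men with "known metastatic disease planned to start and change systemic therapy regimen". Section 4.1.1 has no metastatic route; its disease-state entries are "Patients already diagnosed with prostate cancer: Primary Staging: intermediate and high-risk patients per NCCN guidelines" and biochemical recurrence. Section 4.5.3 expects 100 patients with "primary diagnosis of prostate cancer or biochemically recurrent prostate cancer".

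**Scans.** On the tracer, section 4.2.3 says "It will be administered a single time intravenously prior to the PET imaging". Section 6.2.11 says "A total of 100 patients are planned for exposure to a single dose of" it. Appendix A marks PSMA imaging on the day of the scan only. Under section 4.4 the reader compares the PSMA findings "with the results from previously performed standard-of-care imaging for prostate cancer staging" and notes whether suspicious sites are present. No response category is recorded.

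**Results.** Section 3.1.2 reports how often PSMA scans are positive, by the PSA value before the scan and against conventional imaging, with 95% confidence intervals and no split by indication. Section 4.5.2 gives the management-change rate over everyone imaged, and adds that it "will also be estimated within each group (initial staging, biochemical recurrence, and pre/post treatment". The third of those groups is not defined. No objective, endpoint or analysis measures treatment response.

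**The concern.** For a man being staged, or one with a rising PSA, a positive PSMA scan is a detection. Comparing it with routine imaging asks which method finds more. For a man scanned to assess response, therapy has by definition been given, and it may fall between the earlier imaging and the PSMA scan. A negative scan may then mean that treatment worked, and his PSA may be low for the same reason. Putting both kinds of men into one positivity figure gives a number with no single meaning, and section 3.1.2 provides nothing to separate them. At stake are the declared comparison of PSMA PET with conventional imaging and the relation of positivity to PSA.

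**Working it through.** The plan has no figure to reproduce, because section 4.5.3 waives sample size and power. The check is mainly one of reasoning.

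**1. What study scans can show.** One PSMA scan per man gives zero before/after differences with the same tracer. The only image comparison named is the PSMA scan against earlier routine imaging.

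**2. What that comparison contains.** For one man, let P1 be the PSMA result (1 positive, 0 negative) and C0 the earlier conventional result. Let C1 be what conventional imaging would have shown on the day of the PSMA scan, which is not observed. Then

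P1 − C0 = (P1 − C1) + (C1 − C0).

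The first term is the modality contrast that section 3.1.2 is after. The second is change over the interval. It is negative on average if treatment cleared disease, so the advantage of PSMA PET is understated. It is positive if disease progressed, so the advantage is overstated. The documents limit neither the interval nor the therapy within it.

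**3. Effect on the pooled figure.** With n3 response men among 100 and a mean interval change d, the pooled difference shifts by (n3/100) × d. The documents give neither n3 nor d. Taking n3 as 10 to 30 (an assumption), and since d must lie between −1 and +1, the logical ceiling is 10 to 30 points either way. That is a limit, not an estimate.

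**4. PSA.** Section 1 treats PSA suppression as the measure of whether salvage therapy works, and eligibility after radiation is defined from a nadir. PSA after treatment is therefore not on the same footing as PSA at staging or recurrence, yet section 3.1.2 would put both in one positivity-by-PSA summary.

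**5. Why no response should be read across modalities.** With no true disease change, the share of men who look newly positive lies between max(0, s − c) and min(s, 1 − c), where c is conventional yield and s is PSMA positivity. Take c = 10%, the upper limit in section 1 for early relapse at low PSA, and assume s.
- s = 30%: 20% to 30%
- s = 50%: 40% to 50%
- s = 90%: 80% to 90%

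The yield does not come from metastatic men, so this shows direction only.

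**6. Management change.** Pooled rate = (n3 × p3 + (100 − n3) × 0.40)/100, with all inputs assumed.
- n3 = 10, p3 = 0.6: (6 + 36)/100 = 42%
- n3 = 30, p3 = 0.6: (18 + 28)/100 = 46%
- n3 = 30, p3 = 0.8: (24 + 28)/100 = 52%
- p3 = 0.4: 40%, no shift; p3 below 0.4 lowers the rate

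This shows how case mix moves a weighted mean. It does not demonstrate bias.

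**7. Precision after separating the group.** Half-width at a 50% rate = 1.96 × √(0.25/n).
- n = 100: 9.8 points
- n = 90: 10.3 points
- n = 70: 11.7 points

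**The case against.** The best reply is that this is an access protocol and response is only one reason for referral. That stands. A reader might infer that the study has a response endpoint it cannot deliver, but no response result is planned. Section 4.5.2 reports change in management, and the Synopsis also lists PSA and clinical assessment. A PSMA scan obtained outside the study is not ruled out either.

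A reader might also infer that the pooled management-change rate is biased upward, by as much as 12 points. The documents do not support that. A change prompted by PSMA PET showing more is what the secondary objective sets out to measure. A weighted mean over all patients imaged is correct for the stated denominator, and group rates with intervals are already planned. What remains for section 4.5.2 is attribution: real change since the earlier imaging may be credited to PSMA PET. The clinician survey in section 4.2.2 asks how the scan affected management, which reduces this but does not remove it.

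Double counting of men scanned before and after treatment is not supported, since no passage provides for re-enrolment. Nor do the documents show that effective therapy would be changed wrongly.

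The comparator may also sometimes be another PET tracer, since section 1 treats choline and fluciclovine as routine. That changes the size of the modality term but not the interval term. None of these replies answers section 3.1.2, where no split by indication is planned.

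**Conclusion.** The point holds for section 3.1.2. If response men are enrolled, the positivity results set a scan and PSA that may follow treatment against imaging that may precede it, and pool them with staging and recurrence men. The error can go either way. Its size depends on the number of such men, the interval and the therapy given, and the documents state none of these. The 42% to 52% range illustrates case mix only.

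For section 4.5.2 the point is smaller: an undefined group and an overall rate open to the same question of attribution. Whether the problem arises at all depends on whether the metastatic route belongs to the study, and the Synopsis disagrees on this with sections 4.1.1 and 4.5.3. The change is worth making, but the issue does not undermine the access and safety purpose.

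**What to change.** - **Eligibility.** Reconcile the Synopsis (Population and inclusion criteria) with sections 4.1.1, 4.5.2 and 4.5.3 on whether the metastatic and response route is part of the study.
- **Grouping.** Assign each man's group from the referral indication at consent, before the PET result is known.
- **Section 3.1.2.** Report positivity by group, both by PSA and against conventional imaging. Leave response-indication scans out of the pooled comparison with conventional imaging.
- **Section 4.5.2.** Keep the rate over all patients imaged, define the third group, and add a sensitivity rate without response-indication men.
- **Data and wording.** Record the date of the comparator imaging and any therapy since. State that no response conclusion is drawn across modalities.

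The cost is protocol wording, two recorded items and a smaller denominator for one pooled comparison. The screening chart review, and the concomitant medications that section 6.2.8 enters in the medical record, may already hold the two items. With 10 to 30 of 100 men set apart (assumed), the half-width grows by 0.5 to 1.9 points (10.3 − 9.8 and 11.7 − 9.8).

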1. BACKGROUND AND RATIONALE

In the past several years, there has been an increasing volume of patients in the United States (US) who undergo open radical prostatectomy or robotic-assisted radical prostatectomy for high-risk prostate cancer. Based on several published retrospective reports [1, 2], there may be evidence of improved disease-free survival outcomes for this high-risk cohort compared to outcomes obtained with conventional radiotherapy approaches in conjunction with long-term androgen deprivation therapy. Concomitant with these practice trends in the US, there has been an increasing number of referrals for salvage radiotherapy due to the manifestation of detectable prostate-specific antigen (PSA) levels, which become apparent after surgery. The observation of an increased number of cases with relapsing disease is not surprising, as the risk of biochemical failure among patients with high-grade disease or other high-risk factors treated with surgery alone have ranged from 40-80% in published reports [3-5]. While such patients are often subsequently treated with salvage radiotherapy, the likelihood of maintaining an undetectable PSA at two years after such treatment is often less than 40% in treated patients [6, 7]. As evidenced from the relatively low biochemical control rates for this cohort of patients, we believe that a significant percentage of patients do not benefit from salvage radiation therapy (SRT) using standard treatment techniques because of the presence of extra-pelvic micro-metastatic disease. The increasing number of high-risk patients who develop relapsing disease after surgery currently represents a serious clinical problem. Thus, superior imaging modality for advanced newly diagnosed prostate cancer is clearly needed.

The primary barrier and challenge facing urologic oncologists is the accurate identification of the source of the rising PSA in the post-prostatectomy setting. Current imaging modalities do not perform with high sensitivity, as far as detecting local or regional recurrence with sensitivity or specificity. This concern is further compounded by the fact that several reports have demonstrated that SRT is more effective in achieving durable PSA suppression when treating patients with lower PSA baseline levels. Based on published guidelines [4-8], SRT is routinely administered to patients with the manifestation of a rising detectable PSA, which is often noted at levels of 0.1-0.5 ng/ml. Especially at these low PSA levels indicative of early relapse, standard imaging studies such as MRI, CT scans, and bone scans are often associated with a low yield of detecting positive imaging findings of < 10% and it is unclear if the more recent use of whole body MRIs provide any further information as to the sites of metastatic disease especially in the setting of early biochemical relapse. Clearly, improved and more sensitive imaging modalities are desperately needed to help identify patients with early disease relapse that is non-metastatic, who would then be suitable candidates for local-regional SRT.

We can hypothesize that the use of PSMA PET imaging will provide information about the site of recurrence that can be used to select patient for SRT and adjust SRT target volumes. It should be noted that especially for high-risk patients with biochemically relapsing disease, routine staging work-up would include bone scan and CT/MRI imaging. Nevertheless, the yield on these studies in the setting of early relapse disease has been low.

Although choline or fluciclovine have improved our ability to detect recurrent and metastatic prostate cancer by interrogating the metabolome that is upregulated in prostate cancer. Specifically, fluciclovine (¹⁸F) uptake is related to increased amino acid transport that has been demonstrated to occur with

prostate cancer (14). Both C-11 choline and fluciclovine (18F) are now FDA approved and have become a de-facto standard of care. Yet, there are additional cell level imaging biomarkers that are also upregulated in prostate cancer and may be exploited for imaging. One of these promising new targets is prostate specific membrane antigen (PSMA) (15). PSMA is a Type 2 transmembrane glycoprotein of the M28 peptidase family and is significantly overexpressed on the cell surface of prostate cancer (16,17). PSMA therefore provides a promising target for PC-specific imaging and therapy. ⁶⁸Ga-labelled PSMA ligand suggests that this novel tracer can detect PC relapses and metastases with high contrast by binding to the extracellular domain of PSMA, followed by internalization. A meta-analysis published in 2016 (9) describing 18 studies with efficacy and safety, 5 of which, with histopathology correlation of the positive lesions, reported an improved sensitivity and specificity of PSMA radiolabeled with ⁶⁸Ga (⁶⁸Ga-PSMA-HBED-CC or [⁶⁸Ga]-PSMA-11) over choline.

Evidence has demonstrated the superiority of ⁶⁸Ga-PSMA-11 PET/CT in staging of the high or intermediate risk prostate cancer patients (18, 19-22). In one study, ⁶⁸Ga-PSMA-11 PET/CT showed considerable change in staging and management of prostate cancer patients compared to conventional staging (19). The findings of this study supported the replacement of the conventional Bone scan and CT by ⁶⁸Ga-PSMA-11 PET/CT (19). In a prospective study, it was reported that ⁶⁸Ga-PSMA-11 PET/CT changed the disease stage in 69% of the patients (18). It was concluded that ⁶⁸Ga-PSMA-11 PET/CT can greatly impact the staging and management of prostate cancer patients outside the two classic indications (biochemical recurrence and pre-surgical staging) (18). A recent review of 11 studies including 904 patients represented ⁶⁸Ga-PSMA-11 PET/CT as a promising test for preoperative lymph node staging in intermediate/ high risk patients with prostate cancer (20, 21) . The results of the largest high-risk cohort for primary prostate cancer staging with ⁶⁸Ga-PSMA-11 PET/CT have recently been published (21). In this study comprising 691 newly diagnosed high-risk prostate cancer patients, ⁶⁸Ga-PSMA-11 PET/CT detected the advanced disease in 35 percent of the patients (21). The specificity for lymph node metastasis detection on ⁶⁸Ga-PSMA-11 PET/CT in the pelvic lymph node dissection cohort has been reported to be very high (96.6%) (21). A study on 1253 men was conducted to assess the risk of metastatic disease on ⁶⁸Ga-PSMA-11 PET/CT at prostate cancer diagnosis and the results supported the use of ⁶⁸Ga-PSMA-11 PET/CT to detect metastasis and staging (22). Finally, A multicenter, two-arm, randomized study has been conducted and investigated whether ⁶⁸Ga-PSMA-11 PET/CT has improved accuracy when compared to the conventional imaging (CT and bone scan) (23). Collective data from this study and others provide evidence that ⁶⁸Ga-PSMA-11 PET/CT is better and can replace conventional imaging with bone scan and CT for staging patients with high-risk prostate cancer before surgery or radiotherapy.

There is *significant clinical need* to provide high risk prostate cancer patients and those with biochemical relapse access to ⁶⁸Ga-PSMA-11 PET imaging, and because of the exceptional performance that this imaging has shown for prostate cancer staging and the detection of recurrent prostate cancer, it has clear potential to transform clinical management of patients with prostate cancer. While FDA recently approved ⁶⁸Ga-PSMA-11 at UCSF and UCLA, it is not approved beyond these two institutions and is not currently commercially available. This generates the need for a study at the University of Colorado Anschutz for expanded access use.

Similarly, the ¹⁸F PSMA binding ligand, 18F DCF-Pyl (PYLARIFY® or piflufolastat F 18), has shown high accuracy in detection of prostate cancer in the above indications (24, 25) and recently received FDA

approval. This compound, however, has not been yet made commercially available to patients by the sponsor (Lantheus), again emphasizing the need for this study for expanded access use.

